## DISCUSSION

This study will provide externally validated prognostic models for risk of prolonged sickness absence in workers on sick leave due to MSDs. This will be explored using three different outcomes of prolonged work absenteeism over a 1-year follow-up [36,90]. The models will be developed using predictors that are selected on the grounds of the best available evidence and clinical acceptability, which ensures that

the model development is based on existing evidence of importance and validity. This approach ('full-model approach') will also minimise the potential overfitting of the new models [37,76]. To our knowledge, this study will also be the first to assess the clinical usefulness of a prognostic model for predicting prolonged sickness absence. If the models show good predictive performance, we plan to create an online risk calculator that provides risk individual estimates, which automates the complex modelling methods using an interactive graphical interface. Essentially, before we develop a web-based risk calculator, we will consider issues regarding privacy and data storage, as well as transparent reporting of model equations and possible model changes over time [91].

Statistical analysis plan (SAP) for:

**Modifiable prognostic factors of high costs related to
healthcare utilization and productivity loss among people on
sick leave due to musculoskeletal disorders (working title)**

Project The MI-NAV project

NCT number NCT04196634

Document date 25.08.2022

1. Introduction

Scope

This document is a supplement to the MI-NAV protocol (ClinicalTrials.gov Identifier: NCT04196634) and comprises a statistical analysis plan (SAP) for the article “Modifiable prognostic factors of high cost related to healthcare utilization and productivity loss among people on sick leave due to musculoskeletal disorders”. The current SAP has been written after data collection was finished. However, the SAP will be uploaded to ClinicalTrials.gov before we enter the study database for the subsequent analyses.

2. Administrative information

Version of SAP

1.0

Study sponsor

This study is part of the MI-NAV project, a large-scale project funded by the Research Council of Norway, through the program “Sickness absence, work, and health” (280431/GE).

Contributors to SAP

Name	Title	Role
[name] ^{1,2}	[name]
[name] ¹	PhD-student	Main author of SAP
[name] ³	[name] to SAP
[name] ^{4,1}	PhD	Contributor to SAP
[name] ¹	PhD-student	Contributor to SAP
[name] ¹	PhD-student	Contributor to SAP

¹Oslo Metropolitan University, ²Oslo University Hospital, ³Vrije University Amsterdam, ⁴Diakonhjemmet Hospital

Signatures

I hereby declare that I have reviewed and approved the statistical analysis plan for this study

[name]
Main author of the SAP

[name]
Principal Investigator

3. Study aim

The primary aim of this study is to identify modifiable prognostic factors of high costs related to healthcare utilization and productivity loss among people on sick leave due to musculoskeletal disorders. A secondary aim is to identify modifiable prognostic factors of high costs related to separately 1) healthcare utilization, and 2) productivity loss.

4. Method

Design and setting

A prospective observational cohort study with one year of follow-up was conducted within the Norwegian Labour and Welfare Administration (NAV). This cohort study [1] is part of a large-scale project; the MI-NAV project (ClinicalTrials.gov Identifier: NCT04196634).

Study population and recruitment

Eligible participants were people, aged 18 to 67 years, on sick leave (50-100% sick leave rate, ≥ 4 weeks) due to musculoskeletal disorders (diagnosis within the musculoskeletal (L) chapter of the International Classification of Primary Care, 2nd edition (ICPC-2)[2]). Exclusion criteria were insufficient Norwegian or English language skills to participate in the study. Participants were invited through a link on the participants' individual profile page on the NAV website between November 2018 and February 2019. Participants entering the link were asked to consent digitally.

Data collection, outcome, modifiable prognostic factors, and covariates

At baseline, all participants responded to an electronic questionnaire including demographic variables and a set of patient-reported measures. Data on healthcare utilization were collected from public records including the Norwegian Patient Registry (NPR) and the Municipal Patient and User Registry (KPR). Data on productivity loss were collected from public records (NAV), containing dates and grading of absenteeism as well as the related diagnostic code. Data on healthcare utilization and productivity loss were collected in the period from baseline to 3 months retrospectively, and in the one-year follow-up period. All information is stored and will be analysed securely through the Service for sensitive data (TSD) at the University of Oslo, Norway.

Outcomes

The primary outcome of this study is costs related to healthcare utilization and productivity loss aggregated for one year of follow-up and dichotomized as high or low. Having high costs is defined as patients with costs in the top 25th percentile [3, 4]. As noted above, healthcare utilization was collected from public records (NPR, KPR) and included: consultation with healthcare professionals (type and frequency), consultations in emergency room, outpatient activity, number of days of hospitalization and/or institutionalisation, and surgery. Healthcare utilization during the one year of follow-up will be described as shown in Table 2. The total cost of healthcare utilization will be estimated based on reimbursement rates collected from NPR and KPR. Productivity loss was collected from public records (NAV) and included productivity loss related to absenteeism. The total costs of productivity loss will be estimated based on the number of days with absenteeism adjusted for the percentage of absenteeism and multiplied by the average wage rate (from official statistics) in Norway by sex and age groups.

Secondary outcomes of this study are costs related to separately 1) healthcare utilization aggregated for one year of follow up and dichotomized as high and low, and 2) productivity loss aggregated for one year of follow up and dichotomized as high and low.

Modifiable prognostic factors

Potential modifiable prognostic factors are factors expected to have the potential to be modified or improved by appropriate care or treatment, and therefore classified as modifiable. Potential modifiable prognostic factors of high costs related to healthcare utilization and productivity loss are based on previous scientific literature on patients with back pain primarily [3-11], as well as people with musculoskeletal disorders [12-15] and non-diagnosis-specific studies [16-23], and includes the following self-reported variables measured at baseline:

- Pain severity [3-7, 12-15] measured by the numeric rating scale (NRS) [24] from the Keele STarT MSK tool (STarT MSK) [25]
- Disability [3-8, 11, 13-15] measured by a single item (Q4) from the Musculoskeletal Health Questionnaire (MSK-HQ) [26]
- Health-related quality of life [7, 12] measured by the EuroQol 5 dimensions (EQ-5D-5L) [27]
- Emotional well-being [3, 4, 8-10, 14] measured by a single item (Q11) from the MSK-HQ [26]
- Sleep quality [21, 22] measured by a single item (Q4) from the Örebro Musculoskeletal Pain Screening Questionnaire Short Form (ÖMPSQ-SF) [28]
- Health literacy [23] measured by a single item (Q12) from the MSK-HQ [26]
- Future disease expectation measured by a single item (Q6) from the STarT MSK [25]
- Return to work expectancy measured by a single item (Q8) from ÖMPSQ-SF [28]
- Work satisfaction measured by a single item (numeric rating scale, 0=not satisfied, 10=satisfied)

Covariates

Prognostic factor research may vary depending on context (time, place, healthcare setting) and characteristics of the study population. We therefore plan to adjust for potential covariates when evaluating the modifiable prognostic factors. Potential covariates are based on previous scientific literature (as described above), and include the following self-reported variables measured at baseline:

- Sex [5-7, 11, 15-19]
- Age [5, 7, 11, 13, 15, 16, 18, 19]
- Education level [5, 8, 17, 20] measured as the highest education completed, and categorised into low vs. high (university level)
- Pain duration [3, 15] measured by a single item (Q1) from the ÖMPSQ-SF [28]

In addition, the following public records variables will be included as covariates:

- Absenteeism-related diagnosis type at baseline collected from the NAV registry and categorized into “upper/lower limb conditions”, “back and neck conditions”, “joint/inflammatory conditions”, “injury or trauma” or “other MSK conditions”
- Total costs related to healthcare utilization during a period of 3 months prior to inclusion. Healthcare utilization prior to inclusion was collected from public records (NPR, KPR) as described above. Total costs of healthcare utilization will be estimated as described above.
- Total costs related to productivity loss during a period of 3 months prior to inclusion [12, 14]. Productivity loss prior to inclusion was collected from public records (NAV) as described above. Total costs of productivity loss will be estimated as described above.

Other variables

Included participants will also be described with respect to the following baseline characteristics: mother tongue, days of absenteeism one year prior to inclusion, and healthcare utilization prior to inclusion.

Sample size

This study contains secondary analyses embedded in the MI-NAV project. Details on sample size calculation are provided in the MI-NAV protocol [1]. To determine statistical power of this study we used number of events per parameter (EPP) [46-50] and the rule-of-thumb of “10 events per parameter included” [51-54]. With a fixed sample size of 549 participants included in the MI-NAV project, we anticipate 137 participants to be in the top 25th percentile of costs and categorised as having high costs (yes/no) (events). An EPP of 10 will allow a maximum of 13 parameters to be included in the final multivariable prediction model.

Statistical analyses

General analysis considerations

All analyses described in this SAP are considered a priori in that they have been defined in the protocol and/or in this SAP. All post hoc analyses will be identified as such in the article if relevant. All analyses will be carried out using SPSS or Stata and controlled by a senior researcher/statistician. We consider our study as explanatory. Thus, no correction for multiple testing will be performed and p-values < 0.05 will be considered statistically significant. All statistical tests will be two-sided. All confidence intervals will be reported as 95%. Preliminary analyses assessing the influence of missing data and assumptions of normality for continuous variables will be conducted. The assumption of normal distribution will be investigated using histograms and QQ-plots. Normally distributed data will be presented with means and standard deviations (SDs), skewed data with medians and interquartile range (IQR). Categorical data will be reported as counts and percentages.

Description of study flow

The flow of participants through the study will be reported with a flow chart according to the REMARK guidelines [29]. Reasons for dropout will be provided where known. Differences between responders and non-responders will be evaluated.

Missing data

We anticipate few missing values within this study. Information on the primary and secondary outcome will be obtained from public records (NRP, KPR, NAV) where all individuals receiving any form of benefits are registered by their social security number. Furthermore, we anticipate no or minimal missing data for the majority of the potential modifiable prognostic factors and the covariates, as a requirement to answer all questions on key questionnaires was implemented in the electronic baseline questionnaire. Nevertheless, missing value pattern will be visually explored and handled by multiple imputation if relevant (if >5% data is missing).

Participant characteristics

Baseline characteristics of included participants will be presented as shown in Table 1.

Healthcare utilization, productivity loss and cost estimation

Type and frequency of use of different healthcare resources will be calculated for the one-year follow-up period. Healthcare utilization will be presented as shown in Table 2. Costs related to healthcare utilization will be estimated based reimbursement rates collected from NRP and KPR. Days of absenteeism will be calculated for the one-year follow-up period and adjusted for percentage of absenteeism. Cost related to productivity loss will be estimated based number of days with 100% absenteeism and national average wage rates (from official statistics) in Norway by sex and age groups. All costs will be presented in euros (€) 2020 and estimated with both mean and median values with 95%CI, using bias-corrected and accelerated (BCa) bootstrapping as presented in table 3. The BCa will be conducted with a bootstrap sample size of 1000. Cost data are commonly skewed,

thus both mean and median values will be presented to support the result interpretation. Values in Norwegian kroner (NOK) were recalculated to euros using the exchange rate from February 2020 (1€=NOK 10).

Identification analysis

Univariable and multivariable binary logistic regression models will be used to investigate associations (crude and adjusted for selected covariates) between each predefined modifiable prognostic factor and costs related to 1) healthcare utilization and productivity loss, 2) healthcare utilization, and 3) productivity loss. The cost score will be entered into the model as a dependent dichotomous variable (high cost defined as patients with cost in the top 25th percentile, yes/no). Non-linear relationships in the modelling process will be explored using cubic splines or multivariable fraction polynomials, as these are recommended approaches for modelling continuous prognostic factors in prognosis research [30]. The results will be presented as crude and adjusted odds ratios (OR) with 95% confidence intervals (CI) as shown in table 4.

Sensitivity analysis

To assess credibility of the total cost calculation related to the primary analyses, the calculation will be conducted without outliers. Outliers will be identified with simple scatterplots by visual inspection and defined as patients with remarkably high total costs. If multiple imputation on missing data is conducted, the univariable and multivariable logistic regression analyses related to the primary analyses will be performed on complete case data to test credibility of the imputation procedure.

6. Ethics approval

This study is a part of the MI-NAV project [1]. The MI-NAV project (ClinicalTrials.gov Identifier: NCT04196634) has been classified as a quality assessment study by the Norwegian Regional Committee for Medical Research Ethics (reference no. 2018/1326/REK sør-øst A) and approved by the Norwegian Social Science Data Service (reference no. 861249) in 2018.

Table 1. Participants characteristics and clinical status at baseline

	All participants (n=549)	Missing, n (%)
Female, n (%)		
Age in years		
Education at university level, n (%)		
Mother tongue Norwegian, n (%)		
Days of absenteeism last year*		
Diagnosis (ICPC-2)**, n (%)		
Upper limb conditions		
Lower limb conditions		
Neck conditions		
Back conditions		
Joint or inflammatory conditions		
Injury or trauma		
Other MSK conditions		
Pain severity average last week (NRS, 0-10)		
Pain duration, n (%)		
< 3 months		
3-6 months		
> 6 months		
Disability (MSK-HQ, Q4)		
Health-related QOL (EQ-5D-5L, -0.59-1)		
Emotional well-being (MSK-HQ, Q11)		
Sleep quality (ÖMPSQ-SF, Q4)		
Health literacy (MSK-HQ, Q12)		
Future disease expectation (STarT MSK, Q6)		
Return to work expectancy (ÖMPSQ-SF, Q8)		
Work satisfaction (1-10)		
Healthcare utilization prior to inclusion***		
Primary care consultation last 3 months, n (%)		
General practitioner		
Physiotherapist		
Chiropractor		
Emergency room		
Secondary care consultation last 3 months, n (%)		
Outpatient activity		
Hospitalization (non-surgery)		
Rehabilitation stay		
Surgery		

EQ-5D-5L indicates EuroQol 5 dimensions; ICPC-2, International Classification of Primary Care 2ed edition; MSK-HQ, Musculoskeletal Health Questionnaire; NRS, Numeric Rating Scale; ÖMPSQ-SF, Örebro Musculoskeletal Pain Screening Questionnaire Short Form; STarT MSK, Keele STarT MSK tool. *collected from the Norwegian Labour and Welfare Administration (NAV) registry, measured as calendar days, and adjusted for percentage of absenteeism. **Absenteeism related diagnoses type at baseline, collected from the NAV registry. ***collected from public records; the Norwegian Patient Registry (NPR), the Municipal Patient and User Registry (KPR), and the Norwegian Control and Payment of Health Refunds Database (KUHR).

Table 2. Healthcare utilization throughout one-year of follow-up

	All participants (n=549)	Missing, n (%)
Primary care		
Patients with primary care consultation, n (%)		
General practitioner		
Physiotherapist		
Chiropractor		
Emergency room		
No primary care consultations		
Numbers of consultations, median (IQR)*		
General practitioner		
Physiotherapist		
Chiropractor		
Emergency room		
Secondary care		
Patients with secondary care consultation, n (%)		
Outpatient activity		
Hospitalization (non-surgery)		
Duration of stay in days, median (IQR)		
Rehabilitation stay		
Duration of stay in days, median (IQR)		
Surgery		
No secondary care consultations		

*Numbers of consultations is calculated on basis of patients who have reported primary care consultations.

Table 3. Costs (€) due to healthcare utilization and productivity loss throughout one year of follow-up (n=)

	Mean (95% CI*)	Median (95% CI*)	Patients with zero cost, n (%)
Healthcare utilization			
Primary care			
Secondary care			
Productivity loss			
Absenteeism			
Total			

*Bias-corrected and accelerated bootstrapping (1000 simulations).

Table 4. Binary logistic regression analyses; individual associations between modifiable prognostic factors and high costs

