### **Source population**

Our prognostic models will be focused on information collected between the initial 4-12 weeks of a sick leave spell due to MSDs. As such, participants of each dataset will be eligible if they at baseline were:

- On sick leave due to a musculoskeletal diagnosis within the musculoskeletal (L) chapter of ICPC-2 [26].
- On sick leave for at least 50% of their contracted work hours for 4-12 consecutive weeks.

Individuals on sick leave for more than 12 weeks at baseline were excluded.

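### The productivity-loss costing has no contracted-hours term, so as written part-time workers are over-costed relative to full-time workers, unless the absence percentage was meant as a share of a full-time post

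*Combined protocol and SAP*

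**What the plan says.** The cost SAP gives the formula twice. Under Outcomes, productivity loss is "estimated based on the number of days with absenteeism adjusted for the percentage of absenteeism and multiplied by the average wage rate", taken from national statistics by sex and age group. Under the heading on healthcare utilization, productivity loss and cost estimation it reads: "Cost related to productivity loss will be estimated based number of days with 100% absenteeism and national average wage rates". The Covariates section carries the same costing over to the three months before inclusion: "Total costs of productivity loss will be estimated as described above".

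Contract size appears nowhere else in that plan. The NAV data are described as "containing dates and grading of absenteeism as well as the related diagnostic code". The Table 1 footnote describes prior-year absence as "measured as calendar days, and adjusted for percentage of absenteeism". Contract size is not among the covariates (Covariates section, Table 4 footnote), and the Sensitivity analysis section covers only cost outliers and complete cases. Part-time workers are eligible. Entry requires a "50-100% sick leave rate" and the only exclusion is language: "Exclusion criteria were insufficient Norwegian or English language skills to participate in the study".

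The prognostic-model SAP draws on the same 549 people. Under Sickness absence data it adjusts days for part-time sick leave and then, as a further step, for contracted hours. Its example is a person in a half-time position, fully sick-listed, who counts as 3.5 days a week. Item 3 of its Sensitivity analysis again names grading and contracted hours as two items.

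**The concern.** Using an average wage in place of individual earnings is an accepted simplification of the price of lost work. Leaving out contracted hours is different, because it changes the quantity of work counted as lost. If the percentage of absenteeism is a share of the person's own contract, a half-time and a full-time worker of the same sex and age group, both fully sick-listed for the same period, receive the same cost although one lost half the hours of the other.

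The outcome is a rank, so an inflated cost can lift a part-time worker into the high-cost group and push out someone with a larger loss. This reaches the primary outcome (combined cost) and the productivity-loss secondary outcome. The definition of the healthcare-only outcome is not affected. Its adjusted odds ratios are, because the adjusted model includes the three-month productivity cost, which is computed in the same way.

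**Working it through.** **1. The plan's own figures.** The cost SAP's Sample size section anticipates 137 high-cost participants: 0.25 × 549 = 137.25. At ten events per parameter, 137/10 = 13.7, rounded down to the stated 13. Both reproduce.

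**2. What the percentage refers to.** The cost SAP does not define it. In the prognostic-model SAP a person in a 50% position can be 100% sick-listed and is then counted at 7 × 1.0 × 0.5 = 3.5 days a week. The 100% must be relative to the person's own contract, with contract size entering as a second factor. The separate listing in its Sensitivity analysis agrees.

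**3. Relative over-costing.** Let D be absence days, g the grading, f the contract fraction and w the wage for the sex and age group.

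- As written: D × g × w
- With contracted hours: D × g × f × w
- Ratio: 1/f, which is 2.0 at f = 0.5, 1.67 at f = 0.6 and 1.25 at f = 0.8

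The wage cancels because everyone in a sex-age group gets the same rate. The choice of wage statistic therefore cannot repair the comparison, and the ratio is the same in calendar days or workdays.

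**4. Three workers, each absent 26 weeks** (calendar days, an assumption for the costing since the plan states no unit there):

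| Worker | As written | With contracted hours |
|---|---|---|
| Full-time, graded 100% | 26 × 7 = 182 | 182 |
| 50% contract, graded 100% | 182 | 182 × 0.5 = 91 |
| Full-time, graded 50% | 182 × 0.5 = 91 | 91 |

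The last two lost the same hours, but the formula costs one at twice the other.

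**5. Ranks.** A percentile cut-off keeps the group at about 137, so errors take the form of exchanges: one person wrongly in, one wrongly out. The number depends on the part-time share, contract sizes and cost distribution, none of which the documents give.

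**6. Illustration only.** The setting was 1,000 simulated cohorts of 549 with the top 137 classed as high cost. Every input is assumed: lognormal absence days (median 75, log-scale SD 1, capped at 365), grading uniform from 50% to 100%, wage SD 12% of the mean, and a small skewed healthcare cost (lognormal, median equal to 8 days' wage, log-scale SD 1). Absence was distributed alike in part-time and full-time workers. Mean number of the 137 places that change hands:

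| Part-time share | All at 80% contract | All at 50% contract |
|---|---|---|
| 10% | 3.2 | 8.7 |
| 20% | 5.6 | 15.9 |
| 30% | 7.4 | 21.6 |
| 40% | 8.7 | 25.6 |

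Other assumed shapes gave other counts. For productivity loss alone, flat distributions of absence days gave up to 55. These figures are neither estimates nor bounds.

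**7. Mean cost in Table 3.** If a full-time-equivalent wage is applied without scaling, and absence is alike in both groups, the mean productivity cost is overstated by 1/(1 − p(1 − f)) − 1 for part-time share p. With p = 0.1 and f = 0.8 this is 1/0.98 − 1 = 2.0%. With p = 0.4 and f = 0.5 it is 1/0.80 − 1 = 25%. It does not apply if the wage average already includes part-time earnings. The ranking problem applies either way.

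**The case against.** The strongest reply is that this is an undefined term and not a demonstrated error. The cost SAP never says what the percentage is a percentage of, and if it is a share of a full-time post no scaling is needed. That stands as a condition on the conclusion. It does not remove the need for a change, since either reading requires a sentence the plan lacks, and the only evidence in the documents about this cohort points to a contract-relative percentage.

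The other SAP is a separate study with its own outcomes and does not bind this one. It cites a 2023 publication, so its present text is later than the cost SAP of 25.08.2022. The cost SAP therefore cannot be said to have departed from an existing rule. The other SAP is evidence about how the data are recorded, and the worked example remains good evidence on that.

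A reader might also infer the base of the percentage from the eligibility wording, by setting "50-100% sick leave rate" beside the other SAP's "On sick leave for at least 50% of their contracted work hours for 4-12 consecutive weeks". The documents do not support that step. The second phrase is the prognostic study's own filter across three datasets, and its Table 1 attaches contracted hours to the two trials and not to the cohort. The inference rests on the half-time example and the separate listing of the two adjustments.

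Finally, the effect on the results may be small. Take a binary factor with 50% prevalence, a true odds ratio of 2.0 and exchanges unrelated to the factor. Three to eleven exchanges then give 1.96 to 1.85, and 36 give 1.56. That is fair as an illustration, but exchanges need not be unrelated to the factors. They involve part-time status, which is not adjusted for, so the direction is unknown too.

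**Conclusion.** The point holds, conditionally. The formula omits contracted hours in both places it is given and in the covariate that reuses it. If the percentage is relative to the person's own contract, a part-time worker is over-costed by exactly 1/contract fraction relative to a full-time worker of the same sex and age group. If it was meant as a share of a full-time post, there is no over-costing and only the definition is missing.

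Two stronger readings are tempting. One is that a known number of the 137 are misplaced, or that the odds ratios are biased in a known direction. The documents contain no part-time share, contract sizes or cost distribution from which to derive either. The other is that the healthcare-only analysis is wholly untouched. Its outcome is, but its adjusted odds ratios use the distorted prior productivity-cost covariate.

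The plan should be changed on this point before the analysis, because a rank-based primary outcome depends on it and the project already describes the adjustment for the same people.

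**What to change.** First, state in the Outcomes section and in the cost-estimation section what the percentage of absenteeism is a share of, whether days are calendar days or workdays, and whether the wage rate is full-time-equivalent and per which day.

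If the percentage is relative to the person's own contract, define cost as days × grading × contract fraction × full-time-equivalent wage. Say in the Covariates section that this also applies to the three months before inclusion. Add the unscaled costing to the Sensitivity analysis section. The prognostic-model SAP offers a partial precedent: its item 3 drops the grading and contracted-hours adjustments.

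The text change is a few sentences, and the cost SAP says it is to be uploaded before the study database is entered. The real cost is data. Contract fraction is not among the NAV fields the cost SAP lists, and data collection has finished. It would have to come from the data the prognostic-model SAP plans to use for this cohort. That plan does not name the source, so availability is inferred. Some values may be missing, and the plan should say whether its missing-data rule covers them. If contract fraction cannot be obtained, keep the present formula and report the over-costing of part-time workers as a limitation.

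### Cost SAP: the only planned check on the cost outcome deletes high-cost patients chosen by eye, which must lower mean cost and says little about the robustness of the dichotomised primary analysis

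*Combined protocol and SAP*

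**What the plan says.** All references are to the cost SAP, filed as the combined protocol and SAP.

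- **Outcomes:** the primary outcome is one-year cost of healthcare use plus productivity loss, split into high and low. "Having high costs is defined as patients with costs in the top 25th percentile".
- **Identification analysis:** "The cost score will be entered into the model as a dependent dichotomous variable".
- **Sample size:** the expected number of cases is stated as follows (the quantity ranked is cost): "With a fixed sample size of 549 participants included in the MI-NAV project, we anticipate 137 participants to be in the top 25th percentile of". The size of the model is capped accordingly: "An EPP of 10 will allow a maximum of 13 parameters to be included in the final multivariable prediction model".
- **Healthcare utilization, productivity loss and cost estimation:** costs are "estimated with both mean and median values with 95%CI, using bias-corrected and accelerated (BCa) bootstrapping". Both summaries are given because cost data tend to be skewed.
- **Sensitivity analysis:** "To assess credibility of the total cost calculation related to the primary analyses, the calculation will be conducted without outliers". The outlier rule follows: "Outliers will be identified with simple scatterplots by visual inspection and defined as patients with remarkably high total costs". The only regression rerun named there is conditional on multiple imputation having been used: "the univariable and multivariable logistic regression analyses related to the primary analyses will be performed on complete case data".

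The section gives no threshold, no blinding of the person judging, no verification of records and no low-side rule. It does not say whether the 25% cut-off is recalculated after removal.

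**The concern.** A sensitivity analysis should vary something that could plausibly change the conclusion, by a rule another analyst could repeat. This one is weak on both counts.

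How many patients go, and which, is decided by looking at the outcome variable. The Scope section has the SAP posted before the database is entered, and General analysis considerations treats its analyses as specified in advance. A judgement by eye does not deliver that.

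Deletion also runs in one direction, so a lower mean is guaranteed whether or not the costing is sound. Meanwhile the choice that shapes the primary regression, the 25% cut-off, is not tested. The other planned sensitivity analysis concerns imputation and may never be run, since the Missing data section expects few missing values. The outlier check is therefore the only planned one on the cost outcome.

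**Working it through.** **Inputs from the documents:** N = 549; high cost = top 25%; 137 events; 10 events per parameter; at most 13 parameters. **Assumed:** the number removed, k, and the shape of the cost distribution. The SAP gives neither.

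**1. The plan's own figures.** 0.25 × 549 = 137.25, giving 137 events. 137 / 10 = 13.7, giving 13 parameters. Both reproduce.

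**2. Who can be deleted.** The k patients with the highest total cost all lie in the top 25% for any k up to 137. Every deletion is a high-cost case; no low-cost patient can be removed.

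**3. Effect on mean cost.** Let r be the average cost of the removed patients divided by the overall mean. The new mean is mean × (549 − k·r) / (549 − k), so the proportional fall is k / (549 − k) × (r − 1). It is positive whenever r exceeds 1, which the rule ensures.

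- k = 5: 5/544 = 0.92%. With r = 3 the fall is 0.92% × 2 = 1.8%; with r = 10 it is 0.92% × 9 = 8.3%.
- k = 27: 27/522 = 5.17%. With r = 3 the fall is 10.3%; with r = 5 it is 20.7%.

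An illustrative simulation used 400 datasets per setting, log-normal costs with log-SD 0.6, 1.0 or 1.4, and three assumptions about the upper tail. The mean fell in every dataset. The average fall was 3% to 33% at k = 5 and 10% to 65% at k = 27. The median fell by only 0.6% to 1.7% at k = 5 and by about 3.5% to 9% at k = 27.

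**4. Effect on the primary regression as planned.** None. The outcome is yes/no, so a cost far above the cut-off counts the same as one just above it.

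**5. If the regressions were rerun without outliers, which the SAP does not state.** The event count would depend on a choice the SAP leaves open:

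| k | Events, cut-off kept | Events, cut-off recalculated |
|---|---|---|
| 5 | 132 of 544 (24.3%) | 136 |
| 14 | 123 of 535 (23.0%) | 133 |
| 27 | 110 of 522 (21.1%) | 130 |
| 55 | 82 of 494 (16.6%) | 123 |

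With the cut-off kept, k = 10 leaves 127 events, and 127 / 13 = 9.8, below the SAP's rule of 10. With it recalculated, 133 − 123 = 10 patients at k = 14 move from low to high cost.

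The odds ratio has no fixed direction of change. Simulated values at log-SD 1.0 and k = 14:

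| Assumed tail | All patients | Cut-off kept | Cut-off recalculated |
|---|---|---|---|
| Same predictor effect throughout | 1.72 | 1.66 | 1.65 |
| Stronger effect in the tail | 1.56 | 1.43 | 1.40 |
| Extreme costs unrelated to predictor | 1.61 | 1.68 | 1.67 |

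**The case against.** The strongest defence is that the check does what it says and no more. Its stated object is the cost calculation. The authors name the regressions when they mean them, in the complete-case sentence, and do not name them here. A fall in the mean is what a trimmed comparison is meant to show, namely how far a few patients drive it. The SAP already reports the median and bootstrap intervals to deal with skew. This stands as far as it goes: showing the pull of a few patients on the mean is legitimate. It does not rescue a rule without a threshold, and the guaranteed fall cannot by itself speak for or against the credibility of the costing.

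The size of the fall is also open to challenge. Productivity cost is days absent multiplied by an average wage over one year, so that part has a ceiling, and the log-normal tails used above may be too heavy. Removing 27 or 55 patients (5% or 10% of 549) is more than one would expect to pick off a scatterplot. Both points stand. They are reasons to read the lower end of the range as the more likely one.

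A reader might infer three stronger things that the documents do not support:

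- **The primary odds ratios are biased.** They are not: the removal appears only under Sensitivity analysis, and the primary analysis keeps all patients.
- **The check attenuates odds ratios.** The SAP does not say that the models are rerun, and if they were, the direction would depend on how the predictor relates to the extreme tail.
- **The deleted patients are genuine high-cost cases.** Some could be registry or costing errors; the plan has no step to tell the two apart.

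Finally, winsorising also lowers the mean, and other cut-offs answer a different question from trimming. That is true. The gain from winsorising is a rule fixed in advance that keeps every patient. The gain from other cut-offs is a test of the choice on which the primary analysis rests.

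**Conclusion.** The concern holds for the sensitivity analysis, not for the primary result. The rule is subjective, one-sided and applied after costs are seen. Up to 137 deletions it can remove only high-cost patients, so mean cost must fall. The amount cannot be fixed from the documents: about 2% to 8% for five patients costing on average 3 to 10 times the mean, and up to 33% under the heaviest simulated tail. The check says little about the primary regression, which ignores distance above the cut-off, and the 25% cut-off itself goes untested.

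This assumes that total cost in the outlier rule means the one-year follow-up total, and that patients are removed from the top down. The number removed and the skew are assumptions throughout. The point is a cheap improvement to a secondary check, not a threat to the main findings.

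**What to change.** - Keep all patients in every analysis. Correct a value only where checking the source record or the costing shows an error, and report how many were corrected.
- Replace visual deletion with a pre-set rule, for example total cost winsorised at the 99th percentile, reported beside the full-sample mean and median.
- Repeat the primary logistic models with high cost defined as the top 20% (0.20 × 549, about 110 events) and the top 33% (0.33 × 549, about 181 events).
- State that the primary regressions are not rerun on a sample with high-cost patients deleted.

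The cost is a change of SAP wording and a few extra model runs. At 13 parameters the top-20% run has 110 / 13 = 8.5 events per parameter, below the SAP's own rule of 10, and should be presented with that caveat; the top-33% run has 181 / 13 = 13.9. A top-10% run would have about 55 events, or 4.2 per parameter, and should be omitted or labelled descriptive.
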